5.1 Analysis Populations

All analyses of safety will be made on the safety population which will be defined as all subjects who are randomized and received treatment at least once during the study. The safety population will be analyzed as per treatment received. Listings of adverse events and incidents will be produced for the "All Subjects" population which includes all subjects that are identified and screened for entry into the study.

Document Name	Statistical Analysis Plan for Study 206233.docx		
Туре	Version	Document Identifier	Effective Date
eldo clinical doc	1.0; CURRENT; Most-Recent; Effective	090032d580d17d34	27-Mar-2017 09:54:18
Reason For Issue	Auto Issue		

Efficacy analyses will be based on the intent-to-treat (ITT) population which will be defined as all randomized subjects with at least one post baseline assessment of efficacy. This will be the primary population for the efficacy analysis which will be performed as per the randomized treatment.

The Per Protocol (PP) population will be a subset of the ITT population. Subjects with a protocol violation that is deemed to affect efficacy assessments in all study periods will be excluded from the PP population. Subjects with a protocol violation that is deemed to affect efficacy assessments in some (but not all) study periods will be part of the PP population, but their data will be excluded from the period(s) affected by the protocol violation for a PP analysis. An analysis on the PP population will be performed for the primary efficacy variable if there is more than 10% difference in the number of subjects evaluable in any of the treatment groups for the ITT and PP populations. A decision on whether a PP analysis will be performed will be made prior to study unblinding.

The following will be considered violations that may lead to the exclusion of data for PP analysis:

- Violation of inclusion or exclusion criteria at screening that may affect efficacy
- Violation of pre-treatment baseline bite force continuance criteria
- Treatment administration errors
- Use of prohibited treatment or medication before or during the study, which is felt will affect the assessment of efficacy
- Weight of denture adhesive applied is outside the range 1 ± 0.05 grams

The following will be included in the review of protocol violations but will be reviewed on a case-by-case basis to determine whether the data should be excluded from a PP analysis:

- Test day visits separated by less than 24 hours will be reviewed on a case-bycase basis prior to database lock to determine if any time points for any of the subjects will be excluded.
- Bite force measurements outside the time window of ±5 mins for the 0.5, 1, 3,
 6, 9 and 12-hour assessments, will be reviewed on a case-by-case basis prior

Document Name	Statistical Analysis Plan for Study 206233.docx		
Туре	Version	Document Identifier	Effective Date
eldo clinical doc	1.0; CURRENT; Most-Recent; Effective	090032d580d17d34	27-Mar-2017 09:54:18
Reason For Issue	Auto Issue		

to database lock to determine if any time points for any of the subjects will be excluded. For the ITT analysis, assessments will be assigned to the nominal visit, irrespective of whether the assessment took place within the time window or not.

Protocol violations which warrant exclusion from efficacy analysis will be identified between the statistician and clinical research director or designee, ahead of database freeze and breaking the study blind.

5.2 Subgroups/Stratification

There are no specific subgroups or strata which need to be considered.

5.3 Time Windows

Time windows for the test day visits and bite force assessments will be reviewed as mentioned above during the blinded data review. According to the protocol there will be at least 24 hours (up to 14 days) between treatment visits to allow recovery from the bite force procedures. Also according to the protocol no post adhesive application bite force measurements will be made earlier than the specified time and not later than 5 minutes after the specified time.

6 Demographics and Baseline Characteristics

6.1 Subject Disposition

The subject disposition summary will include number of subjects screened, randomised, withdrawals (including reason), and the number of subjects in safety, ITT and PP populations. Subject disposition by study period will also be presented.

6.2 Demographics

Summary of demographic information will include age, gender, race and ethnicity. Categorical measures (gender, race and ethnicity) will be summarized by the number and percentage of subjects in each category. Descriptive statistics for age will include the mean, median, standard deviation and minimum/maximum.

6.3 Baseline Characteristics

Baseline bite force data will be summarised as part of the efficacy presentations. No additional baseline characteristics will be presented.

Document Name	Statistical Analysis Plan for Study 206233.docx		
Туре	Version	Document Identifier	Effective Date
eldo clinical doc	1.0; CURRENT; Most-Recent; Effective	090032d580d17d34	27-Mar-2017 09:54:18
Reason For Issue	Auto Issue		

7 Treatment Compliance and Concomitant Medications

7.1 Treatment Compliance

The adhesive will be applied to dentures by one member of the study staff therefore excellent compliance is anticipated. Compliance will not be summarized; however, the instances where the weight of the adhesive used is outside the tolerance windows $(1g \pm 0.05 \text{ grams})$ will be listed for the blinded data review.

7.2 Concomitant Medications

Concomitant medication data will not be presented in the study report. A listing of concomitant medications will be produced for evaluation of protocol violators only.

8 Efficacy Analysis

The ITT population will be the primary population for the analyses of efficacy; a PP analysis will be performed for the primary efficacy variable if there is more than 10% difference in the number of subjects evaluable in any of the treatment groups for the ITT and PP populations. A decision on whether a PP analysis will be performed will be made prior to study unblinding.

For all parametric analyses, all assumptions of normality and homogeneity of variance will be investigated. Violation of these assumptions may be overcome using suitable transformation or performing a non-parametric test (e.g. the Wilcoxon Sign Rank test).

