9.2.3. Criteria for Evaluation

9.2.3.1. Criteria for Assessing Efficacy

Efficacy will primarily be assessed by Area Over Baseline (AOB) over 12 hours for the incisal bite force (lbs) (denoted by AOB₀₋₁₂). The difference will be estimated for each of the test products compared to no adhesive.

Success would be achieved if any of the test products was statistically significantly better than no adhesive. The observed differences for the treatment means will also be considered.

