9.3.2. Primary Analysis(es)

Incisal Bite Force (lbs): Area over Baseline (AOB₀₋₁₂)

Document Name	Project CCI protocol		
Туре	Version	Document Identifier	Effective Date
eldo clinical doc	5.0; Most-Recent; Effective; CURRENT	090032d580cfe581	23-Feb-2017 14:35:47
Reason For Issue	Auto Issue		

The Area Over Baseline (AOB) over 12 hours for the incisal bite force (lbs) (denoted by AOB_{0-12}) is the primary efficacy variable.

To calculate this variable first the Area Under the Curve (AUC) is calculated from 0 to 12 hours (AUC_{0-12}) using the trapezoidal method. AOB_{0-12} will be calculated as (AUC_{0-12})/12 minus baseline bite force (lbs). This transformation will return the measurement to the same scale as the original observations whilst also looking at the average amount of improved force over time by subtracting the baseline value (AOB: Area Over Baseline). Higher values of AOB demonstrate a stronger bite force over time than lower values.

Missing readings will be ignored and interpolation will be made between pre and post the missing values, if necessary. In the case of more than one missing value or if the 12 hour value is missing, the AOB will be set to missing.

An analysis of covariance (ANCOVA) model will be used with AOB values as the response, with fixed effect factors for treatment group, period and subject-level baseline, period level baseline minus subject-level baseline as covariates. Subject will be included as a random effect.

From the above model, treatment differences between groups, (each of the two adhesives versus no adhesive), 95% confidence intervals and p-values, will be provided. The confidence intervals and p-values will be adjusted using the Dunnett's method so that the overall confidence level for the two confidence intervals is maintained at 95% and the two treatment comparisons can be performed with an overall 5% significance level. The assumption of normality and homogeneity of variance will be investigated. Violation of these assumptions may be overcome using suitable transformation or performing a non-parametric test (e.g. the Wilcoxon Sign Rank test).

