3.1. Study Product

The following study products will be supplied by the Clinical Supplies Department, GSKCH:

	Test Product 1	Test Product 2	Reference Product	Negative Control
Product	Test adhesive 1	Test adhesive 2	Super	No adhesive
Name	with a thin	with a thin	Poligrip® Free	_,
	nozzle	nozzle	Adhesive	
			Cream (USA	
			marketplace)	
Product	CCI	CCI	CCI	N/A
Formulation				
Code (MFC)				
Dose	Continuous	Continuous	3 dabs for	N/A
	strips applied	strips applied	upper denture	
	to upper	to upper	as per the	
	denture as per	denture as per	product label	
	the application	the application	application	
	instructions	instructions	instructions	
Route of	Oral topical	Oral topical	Oral topical	N/A
Administrat				
ion				
Dosing	applied to clean	applied to clean	applied to clean	N/A
Instructions	dry denture fit	dry denture fit	dry denture fit	
	surface in a	surface in a	surface in a	
	pattern	pattern	pattern	
	consistent with	consistent with	consistent with	
	the application	the application	the product	
	instructions	instructions	label	
			application	
			instructions	

Document Name	Statistical Analysis Plan for Study 206233.docx		
Туре	Version	Document Identifier	Effective Date
eldo clinical doc	1.0; CURRENT; Most-Recent; Effective	090032d580d17d34	27-Mar-2017 09:54:18
Reason For Issue	Auto Issue		

4 Sample Size Determination

Approximately 25 subjects will be screened to randomize approximately 21 subjects to ensure that approximately 18 evaluable subjects complete the study.

A sample size of approximately 18 subjects completing all treatment periods will provide approximately 81% power to detect a difference of 2.01 lbs in at least one of the two test products from no adhesive, using two-sided t-tests with family wise significance level of 5% based on the Dunnett's adjustment, assuming a residual standard deviation of 1.929 lbs. The estimate of SD is obtained from the study. This was the larger SD among two similar earlier studies:

The delta of 2.01 was obtained from the study. In that study this was the observed difference between Super Poligrip and no adhesive. This was the lowest observed delta for Super Poligrip vs no adhesive among the studies.

As such the expected performance of the test products is completely unknown but we would like at least one test product to perform like Super Poligrip or better.

Power calculations were performed for 2 alternative hypotheses:

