8.1 Primary Efficacy Analysis

Incisal Bite Force (lbs): Area over Baseline (AOB₀₋₁₂)

The Area Over Baseline (AOB) over 12 hours for the incisal bite force (lbs) (denoted by AOB_{0-12}) is the primary efficacy variable.

To calculate this variable first the Area Under the Curve (AUC) is calculated from 0 to 12 hours (AUC₀₋₁₂) using the trapezoidal method. AOB₀₋₁₂ will be calculated as (AUC₀₋₁₂)/12 minus baseline bite force (lbs). This transformation will return the measurement to the same scale as the original observations whilst also looking at the average amount of improved force over time by subtracting the baseline value (AOB: Area Over Baseline). Higher values of AOB demonstrate a stronger bite force over time than lower values.

Document Name	Statistical Analysis Plan for Study 206233.docx		
Туре	Version	Document Identifier	Effective Date
eldo clinical doc	1.0; CURRENT; Most-Recent; Effective	090032d580d17d34	27-Mar-2017 09:54:18
Reason For Issue	Auto Issue		

Missing readings will be ignored and interpolation will be made between pre and post the missing values, if necessary. In the case of more than one missing value or if the 12 hour value or the baseline value is missing, the AOB will be set to missing.

An analysis of covariance (ANCOVA) model will be used with AOB values as the response, with fixed effect factors for treatment group, period and subject-level baseline, period level baseline minus subject-level baseline as covariates. Subject will be included as a random effect.

From the above model, treatment differences between groups, (each of the two adhesives versus no adhesive), 95% confidence intervals and p-values, will be provided. The confidence intervals and p-values will be adjusted using the Dunnett's method so that the overall confidence level for the two confidence intervals is maintained at 95% and the two treatment comparisons can be performed with an overall 5% significance level.

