8.2 Secondary Efficacy Analysis

Incisal Bite Force (lbs): Area over Baseline (AOB₀₋₁₂)

From the ANCOVA model described above, treatment difference for each of the two test adhesives versus Super Poligrip® Free and with each other will be provided along with 95% confidence intervals and p-values. All tests will be conducted at the two sided 5% significance level. If non-parametric analysis is performed for the primary efficacy variable then these secondary comparisons will be performed in a similar way as the primary comparisons.

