- Listing of serious AEs. (if there are none a null listing will be produced, if there are >5 treatment emergent SAEs a table will be produced by SOC and PT)
- Table of Non Serious treatment emergent AEs by SOC and Preferred Term.
 (only produced if there are > 5 SAEs)
- Listing of incidents (if there are none a null listing will be produced)

Document Name	Statistical Analysis Plan for Study 206233.docx		
Туре	Version	Document Identifier	Effective Date
eldo clinical doc	1.0; CURRENT; Most-Recent; Effective	090032d580d17d34	27-Mar-2017 09:54:18
Reason For Issue	Auto Issue		

No inferential analyses will be performed to compare treatments with respect to safety.

10 Interim Analysis

No interim analysis is planned for this study.

11 Topline Summary

The following outputs will be produced for the topline report.

Datasets/Tables	Description
Datasets	STAT1, STAT2
Tables	Table 9.1.1 – Subject Disposition
	Table 9.1.3 – Protocol Violations Leading To Exclusion From Per Protocol Analysis – ITT Population
	Table 9.3.1 – Summary of Bite Force (lbs) by Time – ITT Population
	Table 9.3.2.1 – Summary of AOB by Time – ITT Population
	Table 9.3.2.2 – Summary of AOB (0-12 Hours) – PP Population
	Table 9.4.4 – Listing Of All Adverse Events – All Subjects

The following table will be produced in .rtf format for input into the topline report:

Document Name	Statistical Analysis Plan for Study 206233.docx		
Туре	Version	Document Identifier	Effective Date
eldo clinical doc	1.0; CURRENT; Most-Recent; Effective	090032d580d17d34	27-Mar-2017 09:54:18
Reason For Issue	Auto Issue		

Table 1: Statistical Analysis of Between Treatment Group AOB over 12 hours (ITT Population)

Parameter	Time Point	Treatment Comparison	Difference	Lower CI	Upper CI	P-value
AOB	0-12 hours	Super Poligrip Free vs. No Adhesive	X.XX	X.XX	x.xx	x.xxxx
		Test Adhesive 1 vs. No Adhesive	X.XX	X.XX	X.XX	x.xxxx
		Test Adhesive 2 vs. No Adhesive	X.XX	X.XX	x.xx	x.xxxx
		Test Adhesive 1 vs. Super Poligrip Free	X.XX	x.xx	x.xx	x.xxxx
		Test Adhesive 2 vs. Super Poligrip Free	X.XX	X.XX	X.XX	x.xxxx
		Test Adhesive 1 vs. Test Adhesive 2	x.xx	X.XX	X.XX	x.xxxx

Positive control adhesive: Super Poligrip Free Adhesive Cream (USA); Test Adhesive 1: CC Test Adhesive 2: CC No adhesive [1] From ANCOVA with period and treatment as fixed effects, subject as random effect, and subject-level and period-level pre treatment baseline

bite force (parameterized as period-level minus subject-level) as covariates.

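### Does the rank-test fallback for the primary analysis leave the promised overall 5% unprotected?

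*SAP*

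**What the plan says.** The primary endpoint, AOB over 12 hours, is analysed by ANCOVA with two contrasts: each test adhesive against no adhesive. The sample size (SAP 4) assumes "two-sided t-tests with family wise significance level of 5% based on the Dunnett's adjustment". SAP 8.1 says of the contrasts from the model: "The confidence intervals and p-values will be adjusted using the Dunnett's method". The stated purpose is to hold the pair of comparisons to 5% overall. Either product can carry the study. Protocol 9.2.3.1 reads "Success would be achieved if any of the test products was statistically significantly better than no adhesive", and adds that the observed differences will be weighed too.

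The opening text of SAP 8 requires normality and equal variance to be examined, and continues: "Violation of these assumptions may be overcome using suitable transformation or performing a non-parametric test (e.g. the Wilcoxon Sign Rank test". Protocol 9.3.2 says the same of the primary analysis: "Violation of these assumptions may be overcome using suitable transformation or performing a non-parametric test". Neither document names a diagnostic, a threshold or a decision time for the switch, or a multiplicity method for the rank tests. The commitment in SAP 8 to decide before unblinding concerns only whether a per-protocol analysis is run.

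SAP 8.2 returns to the fallback once. It first sets the secondary tests: "All tests will be conducted at the two sided 5% significance level". It then says "If non-parametric analysis is performed for the primary efficacy variable then these secondary comparisons will be performed in a similar way" as the primary ones. The topline table in SAP 11 is footnoted for the default model only: "From ANCOVA with period and treatment as fixed effects, subject as random effect".

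**The concern.** Dunnett's critical value comes from the joint t distribution of contrasts that share one model and one residual variance. A transformation keeps that model, so Dunnett still applies. Two separate signed-rank tests do not have that joint distribution, so the only adjustment the plan names does not carry over. One significant product is enough for success, so two unadjusted tests give two chances of a false positive. SAP 8.2 does not settle the matter: doing the secondary comparisons in a similar way could mean the same overall error control or only the same type of test.

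The open switch raises a second worry. If nothing fixes when the rank test replaces the ANCOVA, someone could in principle look at both and report the one that succeeds.

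**Working it through.** **Inputs.** 18 completers of about 21 randomized, residual SD 1.929 lbs, difference 2.01 lbs, second product at +1 or 0 lb, two-sided family-wise 5%, at least one product significant (SAP 4; Protocol 9.1 and 9.2.3.1). Each subject receives all four treatments.

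**1. The plan's own figure.**
- SE of a contrast = 1.929 × √(2/18) = 0.643 lbs; 2.01 / 0.643 = 3.13.
- Residual df = (18 − 1)(4 − 1) − 3 = 48. The two-sided Dunnett critical value for two contrasts with correlation 0.5 is 2.28, a per-comparison p of 0.0271.
- Simulated power for at least one rejection: 80.9% (second product +1 lb) and 80.7% (second product 0). The stated figure of about 81% reproduces.

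**2. Two rank tests at 5% each.** All products are set equal to no adhesive, with exact signed-rank tests and 300,000 simulated trials per setting.
- At n = 18 the exact level of one test is 4.83% (reject at W ≤ 40 in either tail). The ceiling for two is 2 × 4.83% = 9.66%. If they were independent it would be 1 − (1 − 0.0483)² = 9.4%.
- The shared control makes the tests correlated. Simulated family-wise error is 8.9% for normal, t (3 df), exponential and lognormal errors alike, and 8.5% at n = 21.
- Two unadjusted t-tests give 9.0%, so the inflation comes from the missing adjustment and not from using ranks.
- Success requires a product to be better than no adhesive. In that direction the figure is about 4.4% at n = 18 with normal errors, against roughly 5% / 2 = 2.5% intended.

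**3. The same tests with the stated 5% kept.** Bonferroni tests each comparison at 2.5%. Holm has the same chance of at least one rejection.
- The exact level at n = 18 is 2.37% per test (W ≤ 34), so the family-wise error cannot exceed 2 × 2.37% = 4.74%. Simulated: 4.5%.
- At n = 21: 2 × 2.39% = 4.78% at most. Simulated: 4.5%.
- The bound holds whatever the correlation between the tests.

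**4. Power.** Moving from Dunnett's threshold to 0.025 costs little: by normal approximation a single comparison has 81.9% power at 0.0269 and 81.2% at 0.025. The adjusted signed-rank tests have 73.4% and 72.5% power under the two alternatives (normal errors, SD 1.929, no period or baseline terms). That is about 8 points below plan (80.9 − 73.4 = 7.5; 80.7 − 72.5 = 8.2). Unadjusted they have 83.5% and 83.1%.

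**5. Is the fallback needed to protect the 5%?** With 60,000 simulations per setting and baseline covariates left out, ANCOVA with Dunnett at n = 18 gives 5.1% (normal), 4.8% (t, 4 df), 4.9% (exponential) and 4.5% (lognormal). In the one unequal-variance setting tried, with the no-adhesive SD half the others, it gives 2.6%. In these settings the default analysis does not exceed its level by more than simulation error.

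**The case for a change.** The best case for amending the plan is that the sponsor thought multiplicity important enough to build into both the sample size and the primary analysis, and a fallback is only useful if it is complete. Naming Holm or Bonferroni would cost a sentence. An adjustment alone also does not close the open switch. If the better of ANCOVA-Dunnett and Bonferroni signed-rank were reported, family-wise error would be 6.5% to 6.9% at n = 18. With unadjusted rank tests as well, it would be about 9.5% (normal) to 10.2% (lognormal).

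The textual gap is real, and so is the 8.9%, given unadjusted tests. The rest carries less weight. Both documents tie the fallback to violated assumptions, so reporting whichever analysis wins would be misuse of the plan and not an application of it.

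Figures for the plan as a whole can be produced by assuming a trigger. With Shapiro-Wilk p < 0.05 on the residuals and an unadjusted fallback they are 5.3% (normal), 6.3% (t, 4 df), 8.1% (exponential) and 8.6% (lognormal). The trigger and the error shapes are assumptions found in neither document. The simulation has no transformation step, and it places the skew directly on AOB, which is a time-weighted average of several readings minus baseline. With the same trigger and Bonferroni the figures are 5.1%, 5.0%, 5.1% and 4.8%.

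A fixed numeric pretest is itself debatable. A normality test covers only one of the two assumptions the SAP names. In the unequal-variance setting above, the Shapiro-Wilk trigger fired only 4.5% of the time.

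**Conclusion.** No change follows. SAP 4 and 8.1 commit the two primary comparisons to an overall two-sided 5%. Dunnett is the means for the default model, and the sentence allowing a rank test does not withdraw the commitment. An analyst who uses the fallback and respects it will split the 5% by Bonferroni or Holm, which gives about 4.5%. Writing that down would only restate what is already promised. The ANCOVA-only table is a template for the default analysis and says nothing about multiplicity in a contingency.

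The exposure is conditional. It is about 8.9% two-sided, or 4.4% in the favourable direction, at n = 18, and only if the rank tests replace the ANCOVA and are run at 5% each. It is nil if the fallback is unused, or if it is adjusted and chosen on the assumptions and not on the result. The cost of keeping the 5% under the fallback is power of about 73% in place of 81%, for normal errors with SD 1.929. These figures assume complete data on 18 subjects and leave out the baseline covariates. The study is a proof of principle that also weighs the observed differences, so a missing detail in an optional step does not put its conclusion at risk.
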